3.2. Study Treatments

Treatments for each group are shown in [Table 1](#).

The treatment period is 36 weeks (252 days), followed by an 8-week (56 days) follow-up period without taking study medication. Subjects will be randomized 1:1:1 to receive placebo, 10 mg avacopan or 30 mg avacopan b.i.d. for the blinded, placebo-controlled treatment for the first 12 weeks (Period 1). Subjects randomized to 10 mg and 30 mg avacopan in Period 1 will continue with the same drug regimen during the next 24-week active drug treatment period (Period 2). Subjects randomized to placebo in Period 1 will be re-randomized to receive either 10 mg or 30 mg avacopan b.i.d. in Period 2. Study treatment-group specific drug kits will be dispensed at relevant study visits. Detailed information about the study drug kits, dispensation and accountability is available in the Study Pharmacy Manual.

Study drug will be taken as described in [Section 5.2](#).

Table 1: Avacopan/Placebo Treatment for the Three Study Groups

	Period 1 (12-Week Placebo- Controlled Treatment)	Period 2 (24-Week Active Drug Treatment)
Group A Placebo	Kit # 1	Re-randomized 50% to Kit # 2 50% to Kit # 3
Group B 10 mg Avacopan	Kit # 2	Kit # 2
Group C 30 mg Avacopan	Kit # 3	Kit # 3

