3.3. Study Flow

Subjects will be screened for eligibility based on the stage of the disease and their health status. The Screening period will be up to 28 days. The primary efficacy analysis can occur when the last enrolled subject has completed the Week 12 visit. After the blinded, placebo-controlled 12-week treatment period, all subjects will continue with a 24-week active treatment with 10 mg avacopan twice daily or 30 mg avacopan twice daily. After Week 36, all subjects will be followed for 8 weeks without receiving study medication.

All subjects will visit the study center during the 28-day Screening period, and, if eligible, on Day 1 and Weeks 2, 4, 8, 12, 16, 20, 24, 28, 32, 36, and 44 of the study. Study drug will be dispensed at the study site and subjects will take the first dose of study drug, i.e., avacopan or matching placebo, while at the study center. Preferably, on visit days subject should take their dose while on-site. Following the first dose, subjects will take study drug twice daily, which will continue for 12 weeks (84 days). Thereafter, all subjects will take avacopan study drug for 24 weeks (168 days), after which they will be followed for 8 weeks (56 days) without taking study drug. Study procedures at each visit day are detailed in the [Time and Events Table](#).

Subjects will exit the study when all the Study Week 44 visit procedures have been completed.

Subjects who experience a flare of HS during the study will be treated by the Investigator, which may include a maximum 1-week course of antibiotic rescue treatment with doxycycline or minocycline or intralesional Kenalog[®] rescue injections (triamcinolone acetonide, 10 mg total maximum per subject within a period no longer than 1 week). These subjects will be requested to remain in the study and to complete all study procedures if possible. During this time, subjects may continue to receive the study drug, if deemed clinically feasible by the Investigator.

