8. STATISTICAL CONSIDERATIONS

8.1. Timing of Analyses

Primary Analysis: This study consists of a 12-week placebo-controlled, double-blind treatment period (Period 1), followed by a 24-week active treatment period (Period 2). When the last subject has completed or dropped out of Period 1, an unblinded analysis of the data collected from Period 1 can be conducted.

To maintain the blinding of treatment assignment in Period 2, the analysis results will be conducted by a CRO and only aggregated results by treatment will be available to the Sponsor. Treatment assignment for individual subjects will not be disclosed to the subject, study site personnel at the site, or the Sponsor until the end of the study.

Final Analysis: When all subjects have completed all of the Week 44 assessments or the last subject has dropped out of Period 2, a final analysis will be conducted on all data collected in the study.

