The purpose of this document is to provide a description of the statistical methods and procedures to be implemented for the analysis of data from ChemoCentryx, Inc. Protocol CL016_168. This document is based on Protocol Amendment 2.0 (31JULY2019). If circumstances arise during the study such that more appropriate analytic procedures become available, the statistical analysis plan (SAP) may be revised. The statistical definitions and analytical methods described in this SAP supersede that in the protocol. Any revisions to the primary endpoint analyses and significant revisions to the secondary endpoint analyses will be made prior to the database freeze for the data in the double-blind treatment period through Week 12. Reasons for such revisions will be described in the final Clinical Study Report (CSR).

B. Protocol and Amendment History

This Statistical Analysis Plan (SAP) is based on 31JUL2019 of Protocol CL016_168, Amendment 2.0.

Version	Approval Date	
Original Protocol	19 October 2018	
Amendment 1	19 March 2019	
Amendment 2	31 July 2019	

II. Protocol Objectives

The study is a randomized, double-blind, placebo-controlled, three-group Phase 2 trial in approximately 390 subjects with moderate to severe hidradenitis suppurativa (Hurley Stage II or III). Subjects will be randomized 1:1:1 to a treatment of 10 mg avacopan twice daily, 30 mg avacopan twice daily or placebo for 12 weeks. Subjects treated with 10 mg or 30 mg twice daily during the blinded, placebo-controlled 12-week treatment period (Period 1, day 1 to week 12) will be followed by an additional 24-week, active treatment period (Period 2, week 12 to week 44) during which they will continue to receive the same dose regimen, either 10 mg or 30 mg avacopan twice daily.

A. Primary

1) Evaluation of the efficacy of avacopan compared to placebo in subjects with Hurley Stage II or III hidradenitis suppurativa (HS) based on subjects achieving a Hidradenitis Suppurativa Clinical Response (HiSCR) after 12 weeks of treatment. HiSCR is defined as at least a 50% reduction in abscess and inflammatory nodule (AN) count and no increase in abscess count and no increase in draining fistula count at Week 12 relative to baseline. Evaluation of the safety of avacopan compared to placebo in these subjects based on the adverse event incidence, changes from baseline in laboratory parameters, and vital signs

B. Secondary

- Evaluation of the efficacy of avacopan compared to placebo in these subjects include:

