The study is a randomized, double-blind, placebo-controlled, three-group Phase 2 trial in approximately 390 subjects with moderate to severe hidradenitis suppurativa (Hurley Stage II or III). Subjects will be randomized 1:1:1 to a treatment of 10 mg avacopan twice daily, 30 mg avacopan twice daily or placebo for 12 weeks. Other systemic treatments for HS including anti-TNF-α treatments are prohibited. Stable antibiotic therapy with doxycycline or minocycline is allowed as specified in the protocol. Subjects treated with 10 mg or 30 mg twice daily during the blinded, placebo-controlled 12-week treatment period (Period 1) will be followed by an additional 24-week, active treatment period (Period 2) during which they will continue to receive the same dose regimen, either 10 mg or 30 mg avacopan twice daily. Subjects on placebo who complete Period 1 will be re-randomized 1:1 to receive 10 mg or 30 mg avacopan twice daily in Period 2. During Period 2 the treatment assignment to 10 mg or 30 mg twice daily will not be disclosed to the subject, study site personnel or the Sponsor. Thereafter, all subjects will be followed for 8 weeks without study drug before they exit the study.

To obtain balance across treatment groups, a stratified randomization scheme will be implemented. The stratification factors and strata within each factor are listed below.

- Hurley Stage (Stage II vs. III):
 - Stage II disease: one or more widely separated recurrent abscesses with tract formation and scars, or
 - Stage III disease: multiple interconnected tracts and abscesses across an entire area, with diffuse or near diffuse involvement.
- Concomitant antibiotic therapy (Yes vs. No)
 - Concomitantly treated with doxycycline or minocycline as the only allowed antibiotic treatment for HS, or
 - No concomitant antibiotic therapy.
- Anti-TNF-α treatment (Treatment naïve vs. Previous treatment):
 - a. Did not previously receive anti-TNF-α drug such as adalimumab or infliximab (anti-TNF-α drug naïve), or
 - b. Previously (but no longer) received an anti-TNF-α drug and
 - completed anti-TNF-α treatment but may have relapsed, or
 - was intolerant to anti-TNF-α treatment, or
 - previously failed to respond or inadequately responded to anti-TNFα treatment.

Not more than 20% of subjects will be in stratum 2a.

For each subject, the study will consist of 4 periods:

- Screening Period (≤ 4 weeks)
- Double-Blind Treatment Period (12 weeks)
- Active Treatment Period (24 weeks)

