Proportion of subjects with a LOR in Period 2 is calculated as those subjects having AN Counts in Period 2 $> 0.5 \times$ (Baseline AN counts —Week 12 AN counts) divided by the total number of subjects in each treatment group in Period 2.

12) Time to LOR during Period 2.

For subjects with LOR, time to LOR (days) = date of LOR – date of the first dose of study drug in Period 2 + 1; For Subjects without LOR or lost follow-up, subjects will be censored at the date of the last assessment of number of HS lesions, i.e., time to LOR (days) = date of last assessment of number of HS lesions – date of the first dose of study drug in Period 2 + 1.

 Proportion of subjects who received add-on antibiotic or other therapy for HS during Period 1 and Period 2 separately.

Add-on antibiotic or other therapies for HS are captured in the Concomitant Medication CRFs.

Proportion of subjects who received add-on antibiotic or other therapy will be calculated as those subjects who received add-on antibiotic or other therapy documented in the CM CRF post baseline divided by the total number of subjects in each treatment group in the safety population.

14) Proportion of subjects who start disallowed opioid pain therapy during Period 1 and Period 2 separately.

Oral and transdermal opioid analgesics (except for tramadol) for any reason are disallowed. Disallowed opioid pain therapy are captured in the Concomitant Medication (CM) CRFs.

Proportion of subjects who start disallowed opioid pain therapy will be calculated as those subjects who start disallowed opioid pain therapy documented in the CM CRF post baseline divided by the total number of subjects in each treatment group in safety population.

15) Proportion of subjects who undergo lesion intervention due to HS during Period 1 and Period 2 separately.

Lesion intervention due to HS is collected in AE and Concurrent Procedures CRFs.

Only two types of interventions are allowed: injection with intralesional triamcinolone acetonide suspension (intralesional Kenalog® rescue injections, i.e., triamcinolone acetonide, 10 mg total maximum per subject within a period no longer than 1 week) and incision and drainage. Any disallowed lesions interventions due to HS other than the two types described above will also be counted as "Lesion intervention due to HS" and will be recorded as major (=CSR reportable) protocol deviation.

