- The Work Productivity and Activity Impairment Questionnaire: Specific Health Problem (WPAI:SHP), change from baseline to Week 12 (MMRM model, ANCOVA model)

For the other endpoints, only the primary analysis will be applied.

For the analysis of variables in Period 1, not by visit, such as: duration of flare, health-economic information on hospitalizations, emergency or urgent care visits,

and lesion interventions for HS, an analysis of covariance (ANCOVA) model with treatment, baseline value, Hurley Stage (Stage II vs. III), concomitant antibiotic therapy with allowed antibiotics (Yes vs. No), and anti-TNF drug use (Treatment naïve vs. Previous treatment) will be applied. Treatment comparisons between the avacopan group and the placebo control group will be presented.

2. Analysis of Secondary and Other Efficacy Endpoints in Period 2

The efficacy data for secondary and other endpoints by timepoint in Period 2 will be summarized using descriptive statistics in the ITT2 population.

For binary variables, Non-Responder Imputation will be used; for change from baseline variables, other than lesion counts endpoints, no missing data imputations will be performed.

For selected secondary efficacy endpoints specified above, a MMRM model including treatment group, visit, treatment-by-visit interaction, and randomization strata (Hurley Stage II or Hurley Stage III, previous anti-TNF-α drug use or anti-TNF-α drug naïve, concomitant antibiotic therapy use or not) as factors, and corresponding baseline as covariate will be applied in Period 2. Testing p-values, point estimates and corresponding 95% confidence intervals will be estimated for the difference the avacopan 30 mg vs. total placebo to avacopan group, and avacopan 10 mg vs. total placebo to avacopan group across visits in Period 2 using linear contrast from the model.

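### The SAP labels Period 2 as Week 12 to Week 44, so a first relapse at the drug-free Week 44 visit can be counted as loss of response in the active treatment period

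*SAP*

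**What the plan says.** SAP section II (Protocol Objectives) gives the bound: "an additional 24-week, active treatment period (Period 2, week 12 to week 44) during which they will continue to receive the same dose regimen".

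The protocol places the end of treatment at Week 36. Section 3.2 says: "The treatment period is 36 weeks (252 days), followed by an 8-week (56 days) follow-up period without taking study medication". Section 3.3 says: "After Week 36, all subjects will be followed for 8 weeks without receiving study medication". The SAP agrees in its own Design Overview (IV.A), where, after the 24 weeks of active treatment, it says: "Thereafter, all subjects will be followed for 8 weeks without study drug before they exit the study". The same section lists the 24-week active period and the 8-week follow-up as two separate periods, and the Study Schedule (IV.E) sets Week 44 in a follow-up column.

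The rules that decide what counts as LOR are these:

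- SAP VI.B, Tables 1 to 3, list Week 44 in the block headed Period 2.
- SAP III, other efficacy endpoints 11 and 12, define LOR and time to LOR for Period 2. They name no last visit, and they stand in a list analysed up to Week 44 where applicable.
- SAP VIII.B item 12 says of subjects without LOR: "subjects will be censored at the date of the last assessment of number of HS lesions". SAP VIII.E.2 repeats this rule for the stratified log-rank tests.
- Protocol 6.13 schedules a lesion count at Week 44.

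**The concern.** LOR in Period 2 is there to show how often a Week 12 improvement is lost during the active treatment period. The drug-free phase asks something else: whether disease returns after everyone has stopped. If the Week 44 count can trigger LOR, one proportion and one time-to-event analysis mix the two questions, and the result would be reported under the label of a 24-week active period.

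Two results are exposed. The LOR proportion during active treatment would be overstated. The 30 mg versus 10 mg log-rank comparison would take in events that arise when neither group is on drug. If those events are about equally frequent in both groups, they dilute any difference between doses.

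The protocol does not resolve this for the programmer, because SAP section I says that the SAP's statistical definitions take precedence over the protocol's.

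**Working it through.** **1. Length of Period 2.** Inputs are the scheduled study days in the protocol's Time and Events Table: Week 12 = Day 85, Week 36 = Day 253, Week 44 = Day 309.

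- Week 12 to Week 36: 253 − 85 = 168 days = 24 weeks. This reproduces the stated length.
- Week 12 to Week 44: 309 − 85 = 224 days = 32 weeks. This does not.
- Off-drug part: 309 − 253 = 56 days = 8 weeks, and 56/224 = 25% of the window.
- Lesion counts after Week 12: Weeks 16, 20, 24, 28, 32, 36 and 44. One of the seven is off drug.

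**2. A subject traced through the rules.** Take a subject with no LOR through Week 36 whose abscess and nodule count crosses the LOR threshold at Week 44. Table 1 maps the visit to Week 44 in the Period 2 block. The LOR definition asks for a qualifying count in Period 2. No rule stops LOR at Week 36 or at last dose, so this is an LOR event. A subject who does not relapse is censored at the same visit.

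**3. Possible size.** The documents give no LOR or off-drug relapse rates, so every rate here is an assumption. Let p be LOR by Week 36 (20% on 30 mg, 30% on 10 mg) and q the proportion of the remainder who first relapse at Week 44, equal in both groups.

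- Reported LOR = 1 − (1 − p)(1 − q)
- Share of events arising off drug = (1 − p)q / reported LOR
- Ratio of cumulative hazards = ln(S30)/ln(S10), where S = 1 − LOR

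| q | LOR 30 mg | LOR 10 mg | Off-drug share, 30 mg / 10 mg | Difference | Hazard ratio |
|---|---|---|---|---|---|
| 0 | 20% | 30% | 0 / 0 | 10 points | ln 0.80/ln 0.70 = 0.63 |
| 10% | 28% | 37% | 29% / 19% | 9 points | ln 0.72/ln 0.63 = 0.71 |
| 30% | 44% | 51% | 55% / 41% | 7 points | ln 0.56/ln 0.49 = 0.81 |
| 50% | 60% | 65% | 67% / 54% | 5 points | ln 0.40/ln 0.35 = 0.87 |

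**4. Dependence on equal relapse.** With q = 50% after 30 mg and 30% after 10 mg, reported LOR is 1 − 0.80 × 0.50 = 60% against 1 − 0.70 × 0.70 = 51%, a reversal. With q = 30% and 50% instead, it is 44% against 65%, a wider gap. LOR rises in every case, but dilution of the dose comparison needs similar q.

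**5. The other reading.** Suppose LOR events stop at Week 36 and only the censoring date runs to Week 44. The log-rank statistic and the Kaplan-Meier estimate change only at event times. With no events after Week 36, the test and the estimates to Week 36 are essentially unchanged, and the curve gains a flat tail.

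**The case against.** The strongest reply is that the SAP does not mean LOR to run to Week 44. It lists follow-up as its own period, its schedule puts Week 44 outside the Period 2 columns, and in section III endpoints 13 to 17 add the follow-up period expressly while LOR does not. Tables 1 to 3 assign visits to windows; they do not define endpoints. A programmer could reasonably stop at Week 36.

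This stands far enough that one should not say the SAP definitely counts off-drug relapse. It does not settle the matter. SAP VIII.B restates items 13 to 16 by Period 1 and Period 2 with no mention of follow-up, so bare Period 2 is already used for a span that section III says includes it. Section II and the tables point the same way.

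Several stronger readings are tempting but not supported:

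- *That the plan fails whichever way Period 2 is read.* Step 5 shows that the Week 36 reading does no harm.
- *That Week 36 counts will be carried into Week 44.* SAP VIII.E.2 says, for change-from-baseline variables, "other than lesion counts endpoints, no missing data imputations will be performed", but it does not name a method for lesion counts. SAP VI.C makes within-period last observation carried forward primary for continuous variables, while VIII.E says observed cases. If follow-up is a separate period, the within-period rule already bars the carry-over.
- *That the Period 2 mixed model averages an off-drug visit in with the others.* The contrast is described as across visits, but the model has a treatment-by-visit interaction and visit-specific contrasts are equally possible.
- *That the dose comparison must shrink because nobody is on drug at Week 44.* Relapse could differ by previous dose (step 4).
- *That stopping at Week 36 isolates response on continued drug.* Protocol 4.4 and 5.7 ask subjects who stop study drug in Period 2 to stay in the study, so some counts before Week 36 are off drug too.

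The consequence is also limited. SAP VI.I treats other endpoints as supportive or exploratory without multiplicity adjustment, and Week 44 events would show as a late step on the planned Kaplan-Meier curves.

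**Conclusion.** The concern holds as a wrong stated bound with a real route into the analysis. The interval in SAP II is 32 weeks, not 24, and the rules as written allow a first relapse at the drug-free Week 44 visit to count as LOR in the active treatment period. The calendar figures (8 of 32 weeks, 1 of 7 assessments) follow from the schedule and need no assumption.

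Counting such relapses can only raise the reported LOR. By how much cannot be derived from the documents, and the table illustrates assumed rates only. Dilution of the 30 mg versus 10 mg comparison depends further on similar off-drug relapse in the two groups. The Week 12 HiSCR analysis and its power are untouched. This should be corrected before the Period 2 analysis is programmed, but it does not threaten the trial's main conclusion.

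**What to change.** - SAP II: change the Period 2 bound to Week 12 to Week 36, in line with the 24 weeks stated in the same sentence and with the Design Overview.
- SAP VIII.B items 11 and 12, and VIII.E.2: count LOR only through the Week 36 visit, and censor subjects without LOR at the last lesion assessment on or before that visit.
- Add a separate off-treatment summary of relapse at Week 44 among subjects without LOR at Week 36.
- SAP VI.B, Tables 1 to 3: show Week 44 under a follow-up heading. Reconcile its target day at the same time: Table 1 gives 197 and Table 3 gives 225, and the schedule gives 309 − 85 + 1 = 225.
- SAP VI.C and VIII.E.2: state that Week 36 values are not carried into Week 44, and that the Period 2 mixed-model contrast covers Weeks 16 to 36.

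The cost is SAP wording and one extra table. No new data are needed.

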6.14. Early Termination Visit

If a subject will be withdrawn early from the study, the following termination procedures must be completed whenever possible:

- A physical examination including body weight;
- Vital signs (temperature, sitting blood pressure, heart rate) after at least 3 minutes of rest;
- A 12-lead ECG will be taken to exclude any clinically significant findings;
- Blood samples for serum chemistry, hematology, and serum pregnancy test (in women of childbearing potential), and PK measurements; the date and time of collection of the PK sample will be recorded;
- Biomarker plasma sample will be collected;

- A urine sample will be collected for urinalysis;
- The anatomic location and number of HS inflammatory nodules, abscesses, fistulae, and hypertrophic scars will be recorded;
- Follow-up photography of lesions will be completed;
- Items for the Sartorius and modified Sartorius scores will be collected if the prior visit where this assessment was made was more than 2 weeks before;
- IHS4 score will be calculated;
- The Investigator will complete the HS-PGA, if the prior visit where these assessments were made was more than 2 weeks before;
- Study personnel will record health-economic information;
- Subjects will be asked to complete the SF-36 v2, EQ-5D-5L, HiSQOL, DLQI, and WPAI:SHP forms, if the prior visit where these assessments were made was more than 2 weeks before;
- Drug accountability will be performed on the returned bottles of study drug;
- Completed daily diary will be collected;
- Any changes in concomitant medication use will be recorded, including alcohol intake, recreational drug use, non-prescription medications, herbal preparations or special diets;
- Any adverse events will be recorded.

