SF-36 v2 and EQ- 5D-5L Patient- Reported Outcomes ⁸			X ³		Х		X	Х			X		X	Х
HiSQOL Index ⁸			X ³		X		X	X			X		X	X
Health-Economic Information ¹³			X ³	X	X	X	X	X	X	X	X	X	X	X
Study drug dispensing			X ³				X			X				
Study drug compliance			X	X	X	X	X	X	X	X	X	X	X	
Study drug accountability ¹¹							X ¹¹			X ¹¹			X ¹¹	
PK plasma sample collection ⁹			X	X	X	X	X	X	X		X		X	X
Concomitant medications	X		X	X	X	X	X	X	X	X	X	X	X	X
Adverse event assessment	Х		Х	Х	Х	Х	Х	X	Х	X	X	Х	X	X

¹Screening period may be exceeded by up to 3 days. Week 1 through 36 visits may occur within a ± 2-day window. The Week 44 visit may occur within a ± 4-day window.

²Physical examination will include body weight measurements. Height will be measured only at Screening.

³These procedures must be performed before taking the first dose of blinded study drug (Avacopan or placebo).

⁴Screening for tuberculosis: see exclusion criteria for specifics.

⁵Subjects will record the maximum severity pain on a numeric rating scale from 0 (no skin pain) to 10 (skin pain as bad as can be imagined) in a daily diary from one week prior to Day 1 through the Week 44 visit.

⁶Twelve body areas will be evaluated to calculate the Sartorius and modified Sartorius scores: left and right axillae, left and right inframammary areas, intermammary area, left and right buttocks, left and right inguinocrural folds, perianal area, perineal area, and other. The presence of nodules, abscesses, fistulae, scars, and other findings will be recorded. The longest distance between two lesions and whether lesions are separated by normal skin will be recorded.

⁷IHS4 score (points) = (number of nodules multiplied by 1) + (number of abscesses multiplied by 2) + [number of draining tunnels (fistulae/sinuses) multiplied by 4]. A score of 3 or less signifies mild HS, a score of 4–10 signifies moderate HS and a score of 11 or higher signifies severe HS.

^{8&}quot;Patient-reported outcomes" (PROs) include the SF-36 v2, EQ-5D-5L, HiSQOL, DLQI, and WPAI-SHP questionnaires. The SF-36 v2 and EQ-5D-5L instruments are widely accepted global non-disease-specific tools to measure changes in subjects' health-related quality of life. The HiSQOL index (an HS-specific instrument) and DLQI instruments are designed to measure the impact of HS or skin disease on subjects' quality of life. The WPAI:SHP assesses the effect of general and specific health conditions on productivity losses.

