Subjects will be asked to take 3 capsules of study drug orally with water and preferably with food every morning, and 3 capsules with water and preferably with food in the evening approximately 12 hours after the morning dose, as instructed. Study drug will be taken for 36 weeks (252 days) continuously.

VI. General Analytical Considerations

A. Baseline and Study Day

Baseline

Baseline for analysis purposes is defined as the last assessment prior to treatment start date/time.

For Subject's Global Assessment of Skin Pain (Numerical Rating Scale, Skin Pain NRS), the average of the last 7 assessments prior to the date of first dose of study drug will be used as Baseline. If there are only 3 to 6 daily assessments available, the average of the available assessments will be used. If there are 2 or less assessments available, the subject's Baseline will be considered as missing.

Change from Baseline

Change from baseline is defined as the post baseline value minus the baseline value. Percent change from baseline is calculated as follows: Percent change = (Change from baseline / Baseline) * 100.

Reduction from Baseline

Reduction from baseline is defined as the baseline value minus the post baseline value. Percent reduction from baseline is calculated as follows: Percent reduction = (Reduction from baseline / Baseline) * 100.

Study Day

Study day for analysis purposes is defined as (date of event – treatment start date) (+ 1 if the event occurs after treatment start date).

B. Analysis Visit Window

All visits including scheduled, unscheduled and early termination visits will be assigned to analysis visits using analysis visit windows based on the actual date the assessment took place. The start day of the analysis window will be calculated as the midpoint between the scheduled assessment and previously scheduled assessment for that parameter. The end day of the analysis window will be calculated as the midpoint between the scheduled assessment and the next scheduled assessment for that parameter. Where multiple measurements for a particular parameter appear within an analysis window, the scheduled visit will be used. If no scheduled visit appears in the analysis window, the result closest to the target day will be used. If equidistant and both are unscheduled and/or early termination visits, the later result will be used for the summary measure.

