Though all measures may not be used in data summaries (e.g., two lab measures within the same analysis visit window), all measurements appear in the datasets and listings. For subjects where the event date is missing, the study day and analysis window will also be missing. See Tables 1-3 below for the analysis windows.

Table 1 Mapping for Endpoints Measured at Study Day 1, Weeks 2, 4, 8, 12, 16, 20, 24, 28, 32, 36, and 44

Scheduled Visit	Target Study Day	Visit Window (Study Day)			
Period 1: Study Day = visit date - date of first dose of study drug in Per 1 +1					
Baseline	1	≤1			
Week 2	15	2 to 22			
Week 4	29	23 to 43			
Week 8	57	44 to 71			
Week 12	85	72 to min (114, the study day of the randomization date for Period 2)			

Period 2: Study Day = visit date - date of first dose of study drug in Period 2 +1						
Entry of Period 2	1	≤1				
Week 16	29	2 to 43				
Week 20	Yeek 20 57 44 to 71					
Week 24	85	72 to 99				

Scheduled Visit	Target Study Day	Visit Window (Study Day)
Week 28	113	100 to 127
Week 32	141	128 to 155
Week 36	169	156 to 183
Week 44	197	≥ 184

Table 2 Mapping for Skin Pain NRS

Scheduled Visit	Target Study Day	Visit Window (Study Day)							
Period 1: Study Day = 1+1	Period 1: Study Day = visit date - date of first dose of study drug in Period 1+1								
Baseline	-1	<1							
Week 2	14	1 to 21							
Week 4	28	22 to 42							
Week 8	56	43 to 70							
Week 12	84	71 to min (113, the study day of the randomization date for Period 2 -1)							
Period 2: Study Day = 2 +1	visit date - date of first	dose of study drug in Period							
Entry of Period 2	-1	<1							
Week 16	28	1 to 42							
Week 20	56	43 to 70							
Week 24	84	71 to 98							
Week 28	112	99 to 126							
Week 32	140	127 to 154							
Week 36	168	155 to 182							
Week 44	196	≥ 183							

Table 3 Mapping for Endpoints Measured at Study Day 1, Weeks 4, 12, 16, 28, 36, and 44

Scheduled Visit	Target Study Day	Visit Window (Study Day)						
Period 1: Study Day = visit date - date of first dose of study drug in Period 1 +1								
Baseline	1	≤1						
Week 4	29	2 to 43						
Week 12	85	44 to min (114, the study day of the randomization date for Period 2)						
Period 2: Study Day	Period 2: Study Day = visit date - date of first dose of study drug in Period 2							
+1	T	Γ						
Entry of Period 2	1	≤1						
Week 16	29	2 to 43						
Week 28	113	44 to 155						
Week 36	169	156 to 197						
Week 44	225	≥ 198						

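### Three interior boundaries in SAP Table 3 contradict the SAP's own midpoint rule, so a few early-termination questionnaires are analysed at the wrong visit or drop out of Week 36

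*SAP*

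**What the plan says.** SAP VI.B gives one rule for all analysis windows. For the start: "The start day of the analysis window will be calculated as the midpoint between the scheduled assessment and previously scheduled assessment for that parameter". For the end: "The end day of the analysis window will be calculated as the midpoint between the scheduled assessment and the next scheduled assessment for that parameter". The windows decide more than routine visits: "All visits including scheduled, unscheduled and early termination visits will be assigned to analysis visits using analysis visit windows". Within a window a scheduled visit takes precedence; failing that, "If no scheduled visit appears in the analysis window, the result closest to the target day will be used".

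The questionnaires have their own table, headed "Table 3 Mapping for Endpoints Measured at Study Day 1, Weeks 4, 12, 16, 28, 36, and 44". The schedule in SAP IV.E places the patient-reported outcomes at exactly those visits, and its footnote says that they "include the SF-36 v2, EQ-5D-5L, HiSQOL, DLQI, and WPAI-SHP questionnaires". Table 3 ends Week 4 at Day 43 and gives Week 12 as "44 to min (114, the study day of the randomization date for Period 2"). In Period 2 it prints Week 16 as 2 to 43, Week 28 as 44 to 155, Week 36 as 156 to 197 and Week 44 as 198 or later.

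Protocol 6.14 creates the off-schedule forms that these windows must place: "Subjects will be asked to complete the SF-36 v2, EQ-5D-5L, HiSQOL, DLQI, and WPAI:SHP forms, if the prior visit" at which they were done lies more than 2 weeks back.

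**The concern.** The rule refers to consecutive assessments of the same parameter. These questionnaires are not scheduled at Weeks 8, 20, 24 or 32, so their windows should be wider than those for the lesion counts in Table 1. Three of Table 3's boundaries instead equal Table 1 cut-points for visits at which no questionnaire is given. The text and the table then assign the same form to different visits, and a programmer cannot follow both.

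The subjects affected are mainly those who leave the study. They have no later scheduled form to take precedence, so their last form can stand as the value of a visit they never reached. SAP VIII.E analyses these instruments with MMRM and with observed-case ANCOVA as a sensitivity analysis, and SAP VI.E adds an ANCOVA of WPAI:SHP change to Week 12. In an observed-case analysis, a Week 7 dropout would count as observed at Week 12.

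**Working it through.** **Inputs.** Target days are those printed in SAP Tables 1 to 3. The 7% attrition and 390 subjects come from Protocol 8.3. The study runs from Day 1 to Day 309, which is 308 days.

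**Formula.** Boundary = (target of one visit + target of the next) / 2, with the midpoint day in the earlier window, as Tables 1 and 2 do.

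**Control.** On their printed targets, the formula reproduces all 9 interior boundaries of Table 1 (22, 43, 71; 43, 71, 99, 127, 155, 183) and all 9 of Table 2 (21, 42, 70; 42, 70, 98, 126, 154, 182). Interior means between post-baseline visits within a period. Tables 1 and 2 print an earlier Week 44 target (197 and 196) than Table 3 (225). That is a separate matter; the check here takes each table's own targets.

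**Table 3.**

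| Boundary | Rule | Printed | Difference |
|---|---|---|---|
| Week 4/12 | (29 + 85)/2 = 57 | 43 | 14 days early |
| Week 16/28 (Period 2 days) | (29 + 113)/2 = 71 | 43 | 28 days early |
| Week 28/36 (Period 2 days) | (113 + 169)/2 = 141 | 155 | 14 days late |
| Week 36/44 (Period 2 days) | (169 + 225)/2 = 197 | 197 | agrees |

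The three failing values are Table 1's splits for Week 4/8, Week 16/20 and Week 32/36.

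**Do forms arise on these days?** With earlier visits on target, yes. Day 44 is 15 days after Week 4 (44 - 29), Period 2 Day 44 is 15 days after Week 16, and Period 2 Day 142 is 29 days after Week 28 (142 - 113). All exceed 2 weeks.

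**What happens to them.**
- Days 44-57 (14 days): a form from Day 50 (Week 7) is 21 days from Week 4 and 35 from Week 12. A dropout has no scheduled Week 12 form, so this form becomes the Week 12 value.
- Period 2 Days 44-71 (28 days): Week 19 is study Day 134, or Period 2 Day 50 if Period 2 dosing starts on Day 85 (134 - 85 + 1). It is 21 days from Week 16 and 63 from Week 28, and becomes the Week 28 value.
- Period 2 Days 142-155 (14 days): a form from Day 150 is 37 days from Week 28 and 19 from Week 36. Table 3 labels it Week 28, where the scheduled Week 28 form normally takes precedence. The form goes unused and Week 36 is left without a value.

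**Size.** 7% of 390 = 27.3 dropouts.
- Analysed at the wrong visit: 27.3 x (14 + 28)/308 = 3.7 subjects, of whom 27.3 x 14/308 = 1.2 at Week 12.
- Losing a Week 36 value: 27.3 x 14/308 = 1.2 subjects.

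**The case against.** The best defence of the printed table is that its two early boundaries keep later data. With Week 4 widened to Day 57, a Day 50 form shares a window with the scheduled Week 4 form and is set aside. Week 12 is then missing under observed case, or is the Day 29 score under LOCF. A dropout's most recent observation gives way to an older one or to none. That cost is real. It does not justify the table: the SAP states no exception for Table 3, and treating a Day 50 form as an observed Week 12 value contradicts the rule the SAP sets. Nor does it cover the third boundary, which is late and withholds a form from the visit it is nearest to. Declaring a deliberate departure in the text would remove the contradiction but leave these effects in place.

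The other defence is low consequence, and it stands. The primary endpoint and the ranked secondary endpoints rest on lesion counts, scores derived from lesions, and pain, none of which uses Table 3. SAP VIII.E does list the questionnaires among selected secondary endpoints, but they are outside the testing sequence in SAP VI.I, which treats comparisons on other endpoints as supportive or exploratory. All measurements remain in the datasets and listings.

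A reader might infer that all 56 affected days (14 + 28 + 14) put a wrong value into an analysis, which would be 27.3 x 56/308 = 5.0 subjects. The precedence given to scheduled visits does not support this: on Period 2 Days 142-155 it holds only for a subject who also missed Week 28. A reader might also count the Day 1/2 edges and the upper limit of Week 12 as errors. Those are pre-dose baseline and period limits, which Table 1 shares.

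**Conclusion.** The contradiction is certain: three of the four interior boundaries in Table 3 do not follow the rule in SAP VI.B, and nothing in either document explains the difference. The match with Table 1's cut-points suggests that they were carried over from that table.

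The effect is small. At most about 4 subjects across the three arms have a form analysed at the wrong visit, about 1 of them at Week 12, and about 1 more loses a Week 36 value. These figures assume that dropouts are spread evenly over the study and that each completes the forms. The second assumption is generous, since Protocol 6.14 asks for the early-termination procedures only where possible and Protocol 4.4 lists loss to follow-up among the reasons for withdrawal. Stray unscheduled forms are not counted. No confirmatory conclusion is at risk. This is a correction worth making because it is cheap and removes an ambiguity for the programmer.

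**What to change.** Before the Week 12 database freeze, correct five cells of SAP Table 3:
- Week 4: 2 to 57
- Week 12: start at 58, upper limit unchanged
- Week 16: 2 to 71
- Week 28: 72 to 141
- Week 36: 142 to 197

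Week 44 (198 or later) is already right. The cost is a small edit to one table, with no effect on trial conduct. The downside is the one described above: some late dropout forms will share a window with a scheduled form and will not be used in the by-visit summaries, though they stay in the listings.
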